## **Remote Ischemic Preconditioning Study / Renal Transplant**

**PI: [name]**

**Co-Investigators:**

### **Specific aim:**

[figure not shown]
Remote ischemic preconditioning (RIPC), a phenotype of ischemic preconditioning, has been found to provide protection from I/R in humans. Several proof of concept clinical trials have shown that transient ischemia reperfusion of lower extremities confers protection to kidneys in patients undergoing endovascular or open surgical repair of an abdominal aortic aneurysm and in patients undergoing cardiac surgery. Furthermore, a randomized pilot clinical trial demonstrated that application of RIPC in high risk patients with kidney dysfunction undergoing coronary angioplasty reduced the incidence of procedure related contrast media induced AKI. To date the efficacy of RIPC in protecting renal allografts from I/R injury during renal transplantation has not been systematically investigated. **In this current proof of concept proposal we will test the central hypothesis that application of RIPC in donors and recipients during live donor kidney transplantation will reduce the severity of graft injury and improve outcome. We propose the following specific aim: To examine the effect of RIPC on clinical and biochemical markers of graft function in patients undergoing live donor kidney transplantation.**

In this study, patients undergoing live donor kidney transplantation will be allocated to the control group or RIPC group. Before allograft implantation, RIPC will be accomplished both in the donor and the recipient by inducing intermittent extremity ischemia through four five cycles of oscillometric blood pressure cuff inflation. The monitored clinical end points will include total urine output following kidney reperfusion over three days, plasma creatinine declination over five days, initiation of dialysis, and development of graft injury. Magnitude of graft injury will be measured using biochemical markers, such as, plasma and urinary concentration of neutrophil gelatinase associated lipocalin (NGAL), IL-18, and KIM-1. By rejecting our null hypothesis, RIPC may serve as a safe, cost-effective protective strategy to prevent allograft injury in the clinical setting of live donor kidney transplantation.

## **2.1 Background**

Kidney transplant is the ultimate treatment for end stage renal disease. It improves the quality of life and survival of the patient. Acute kidney injury (AKI) caused by ischemia reperfusion occurs to some extent in cadaveric renal allografts , invariably in the non-beating heart setting and in some live donor transplants leading to varying degrees of delayed graft function (DGF). DGF due to AKI is defined as the need for dialysis in the first week after transplantation and complicates 4-10% of live donor and 5-50% of cadaveric kidney transplants.i Several lines of experimental evidence suggest that ischemia reperfusion injury (I/R) plays a critical role in the pathogenesis of DGF. The kidney with its high adenosine triphosphate (ATP) consumption and complex vascular architecture is particularly vulnerable to I/R injury. A variety of therapeutic measures have been implemented to decrease the incidence of DGF.ii These measures include maintenance of normovolemia, avoidance of arterial hypotension, and avoidance of nephrotoxic drugs in the recipient. Minimizing cold and warm ischemia time have also been advocated to minimize graft injury; however, these measures have not significantly decreased the rate of occurrence of DGF after kidney transplantation.iii, iv Given the increasing demand for kidney allografts, new diagnostic and therapeutic measures are needed to reduce AKI and DGF following kidney transplant and to improve outcome.v, vi,

## Measures to reduce allograft injury

(Fig#1) STRATEGIES TO MINIMIZE ALLOGRAFT INJURY DURING KIDNEY TRANSPLANTATION

### 2.2.1 Remote Ischemic Preconditioning (RIPC):

Remote ischemic preconditioning (RIPC) represents a novel therapeutic strategy for limiting I/R injury by applying non-lethal episodes of ischemia and reperfusion to an organ or tissue distant from the target organ. vii,viii Przyklenk et al demonstrated brief ischemic episodes of the left circumflex coronary artery significantly reduced myocardial infarct size following sustained occlusion of the left anterior descending coronary artery. ix In subsequent experimental studies, short periods of bowel or renal ischemia conferred protection to the myocardium known as remote inter-organ conditioning. x,xi,xii The discovery that transient ischemia and reperfusion of extremities could also elicit remote ischemic conditioning facilitated translation of this endogenous cardio-protective phenomenon into the clinical setting. Indeed, there is now clinical evidence suggesting this novel form of protection can be achieved by simple inflation and deflation of a blood pressure cuff around the arm. xiii,xiv Several clinical trials examining RIPC in the

setting of percutaneous coronary intervention and coronary artery bypass grafting have shown reduction in myocardial injury. xv, xvi, xvii

### **2.2.2 Ischemic preconditioning: Underlying mechanisms**

The precise mechanism by which brief periods of ischemia reperfusion of remote site confers protection to distant organs is not evident at this time. According to Hausenloy and Lim et al, three main mechanisms –humoral, neural, and systemic –hypothetically interact with each other to confer target organ protection from a remote site. xviii, xix It has been postulated that remote preconditioning result in activation of pro-survival kinase elements of the reperfusion injury salvage kinase (RISK) cascade. The RISK pathway seems important in mediating the protective effects of different pre- conditioning procedures. Activation of some RISK elements in local ischemic preconditioning -P13K, Akt, e-NOS, c GMP, PKG pathways- result in opening of mitochondrial potassium sensitive ATP channels. This in turn leads to reactive oxygen species (ROS) production and potentiation of survival kinase activation. xx

### **2.2.3 Ischemic preconditioning in the animal kidney model**

In a recent meta-analysis, Wever et al examined the efficacy of RIPC in renal ischemia reperfusion injury. xxi Three clinical outcome measures were assessed: serum creatinine, serum BUN, and histologic renal damage. All three outcome measures improved by the application of ischemic preconditioning; however, IPC was more effective when applied twenty four hours before the index ischemia, especially in regards to serum BUN and renal histology. Moreover, IPC was more protective in males than in females. xxii Some inter-species difference was also observed with greater IPC efficacy in mice models as opposed to rat models. xxiii The translation of animal data to the clinical arena is limited because of heterogeneous experimental design and the use of multiple animal species. Serum creatinine was used in multiple studies as a measure of renal function; however, rodent serum creatinine as a measure of renal function is significantly limited by increased tubular creatinine excretion on creatinine in mice. xxiv

[figure not shown]
## 2.2.4 Clinical trials demonstrating protective effect of RIPC on the kidney

Several proof of concept studies have examined protective effects of RIPC in patients undergoing vascular surgery, cardiac surgery, and percutaneous coronary angiography receiving contrast media.xxv,xxvi,xxvii,xxviii,xxix,xxx Two experimental studies showed patients undergoing elective abdominal aortic aneurysm surgery with intermittent cross clamping of the common iliac artery for ten minutes resulted in less postoperative myocardial injury, myocardial infarction, and renal impairment.xxxi Venugopal et al in a retrospective secondary analysis of two RIPC randomized placebo controlled trials found a statistically significant difference in AKI NETWORK staging in patients undergoing coronary artery bypass graft surgery.xxxii Incidences of AKI stages 1, 2, 3 were 25%, 0%, and 0% in the control group and 3%, 8% and 0% in the RIPC group, respectively. This study had several limitations including a highly selective sample population. Patients with renal disease were excluded from original studies, and diabetic patients were excluded from the analysis. Patients at higher risk of AKI, who could potentially benefit from RIPC, were not represented in this study. The study also had limitations inherent to any retrospective analysis. Finally, AKI incidence was not assessed by biomarkers but rather relied on creatinine measurements that can potentially be influenced by extracellular fluid volume distribution and perfusion pressure changes associated with cardiopulmonary bypass (CPB). In a recent double-blinded study, Er et al examined the potential benefit of RIPC on AKI development in patients with impaired renal function receiving contrast medium for elective coronary angiography.xxxiii Half of the patients received transient non-lethal repetitive upper extremity ischemia. The primary endpoint was development of contrast-induced nephropathy (CIN) defined as an increase in serum creatinine  $>25\%$  or  $>0.5/\text{D L}$  above baseline at forty-eight hours after contrast-medium exposure. RIPC resulted in protection against AKI with CIN occurring in 40% of the control group and 12% of the RIPC group, respectively. Levels of urine NGAL at twenty-four and forty-eight hours in both groups with greater increases measured in the control group. There was also a greater increase in serum cystatin-c in the control group at twenty-four and forty-eight hours after contrast administration. Lower levels of serum cystatin-c and urine NGAL were consistent with preserved glomerular filtration rate (GFR) and attenuated kidney injury.

## 2.3 The role of biomarkers in assessment of Graft Injury/Acute Kidney Injury

Reliance on creatinine for the assessment of graft injury is inappropriate because creatinine is a measure of filtration function rather than true injury. Furthermore, serum creatinine is influenced by non-renal factors such as body weight, muscle mass, protein intake, and extracellular fluid volume. Secretion accounts for 10-40% of creatinine clearance, which could mask decreases in creatinine clearance. Most importantly, elevation in serum creatinine shows significant lag time after kidney injury.xxxiv

Multiple novel biomarkers are now available with potential to accurately diagnose graft injury in a timely fashion. There is evidence to suggest that biomarker expression precedes the clinical syndrome of renal failure. Therefore, by measuring kidney specific biomarkers we may identify graft injury before DGF develops.xxxv,xxxvi,xxxvii This may provide a unique opportunity for early intervention including aggressive resuscitation of patients with reversible renal hypoperfusion and early initiation of dialysis in patients with severe ATN based upon biomarker evidence. Indeed, the time delay between graft injury and loss of graft function resulting in serum creatinine elevation may explain the high morbidity and mortality associated with allograft failure. NGAL, IL-18, and KIM-1 have been measured in urine for early diagnosis of graft injury and as markers of graft recovery and function.xxxviii,xxxix, xl, xli, xlii

### **2.3.1 Neutrophil gelatinase associated lipocalin (NGAL)**

Neutrophil gelatinase associated lipocalin (NGAL) is normally secreted by renal tubular cells, lymphocytes, and cardiomyocytes in response to cytosolic or pericellular catalytic iron liberated during ischemic or toxic injury. NGAL released in blood is freely filtered by the glomerulus; however, most NGAL is reabsorbed in the proximal tubule by megalin-dependent endocytosis. This is supported by experimental evidence that systemic injection of labeled NGAL becomes enriched in the proximal tubule but does not appear in the urine of animals.xlvi The presence of urine NGAL is a reflection of proximal tubular injury that precludes NGAL reabsorption and/or increased *denovo* NGAL synthesis. Gene expression studies in AKI have demonstrated massive up-regulation of NGAL mRNA in the distal nephron segments specifically in the thick ascending limb loop of Henle and collecting ducts. This increased synthesis of NGAL in the distal nephron segments accounts for most of the NGAL observed in the urine.xlvi, xlvi Mishara et al examined protocol biopsy specimens in thirteen cadaveric and twelve living- related allografts within one hour of reperfusion for NGAL expression by immunochemistry. Staining intensity for NGAL correlated well with cold ischemia time, peak post-transplant serum creatinine, and requirement of dialysis.xlvi In another study of 33 cases, urine NGAL on the day of transplant surgery was a predictor of DGF with an AUC of 0.9 (Needs reference). Importantly, serum creatinine level peaked after two to four days. Kusaka et al found urine NGAL as a good predictor of recovery from DGF (Needs Reference). In addition, clinical studies suggest that measurement of urine NGAL has several advantages: urine NGAL permits prediction of DGF with adequate urine output and decreasing creatinine, low urine NGAL levels in oliguric patients after kidney transplantation suggests reversible hypovolemia and hypoperfusion, urine NGAL predicts prolonged DGF, and urine NGAL provides a simple non-invasive test to quantify recovery from kidney injury. If urine NGAL reaches a normal value, subsequent rises suggest new kidney injury.xlvi Indeed, emerging evidence suggests urine NGAL is also a marker of chronic kidney disease severity. Urine NGAL levels are elevated in CKD and significantly correlate with serum creatinine, GFR and proteinuria. Levels of urine NGAL in these situations are significantly blunted compared with values measured in AKI.xlvi, xlvi, 1

NGAL limitations include increased sensitivity and specificity in homogeneous patient populations with temporally predictable forms of AKI.

### **2.3.2 Interleukin-18 (IL-18)**

Interleukin-18 (IL-18), a proinflammatory cytokine originating from proximal tubular epithelial cells, is one injury mediator involved in ATN experimental models. Early expression of IL-18 in ischemic, septic and other clinical settings allows for early AKI detection.ii, iii Parikh et al reported IL-18 elevations in AKI patients but not in chronic kidney disease, urinary tract infection, nephritic syndrome, or pre-renal azotemia.iii In critical ARDS patients, urine IL-18 was found to be significantly elevated at twenty-four and forty-eight hours. These values correlated well with patient mortality in ARDS populations; however, IL-18 has inconsistently predicted AKI in post-CPB surgery patients.iv, iv A recent study by Hall et al demonstrates that urine NGAL and IL-18 are accurate predictors of need for dialysis within the first week of kidney transplantation and 3-month recovery of graft function. (needs reference)

### **2.3.3 Kidney Injury Molecule-1 (KIM-1)**

KIM-1 is a trans membrane protein expressed in the proximal convoluted tubule upregulated by toxemic and ischemic insults.iv A cross sectional study by Han et al demonstrated KIM-1 elevations in AKI patients.ivii A comparative analysis of biomarkers in post-CPB patients at two hours found KIM-1 to be a better predictor of AKI as compared to NGAL, IL-18 and cystatin C, but it loses this differentiation at twenty-four and forty-eight hours.iviii, ix Coca et al concluded that KIM-1 cannot predict AKI but is useful in diagnosing established AKI. The combination of KIM-1, NGAL and IL-18 has been found to be a better predictor of AKI.ix A recent study by Malyszko et al showed a strong correlation between KIM-1, serum creatinine, and estimated GFR in renal allograft recipients. (needs reference)

### **3. Significance**

Ischemia –reperfusion (I/R) is inevitable when the kidney allograft is connected with the recipient vascular system initiating a cascade of cellular and molecular events. High energy consumption and a complex vascular pattern make the kidney particularly vulnerable to I/R injury.lxii, lxiii Main consequences of renal I/R injury are allograft injury resulting in primary non-function (PNF) and delayed graft function (DGF). Currently there are a number of strategies pre and post transplantation to attenuate or minimize I/R injury and to improve outcome (See figure# 1). These measures have had minimal impact on the rate of occurrence of DGF.lxiii New approaches are needed to improve recovery and preserve kidney graft function.lxiv, lxv

### **4. Experimental Design**

This will be a randomized controlled trial to evaluate the influence of RIPC administered intraoperatively on the magnitude of allograft injury in patients undergoing live donor kidney transplantation. The study will be conducted after the institutional board approval and informed consent will be obtained from each patient (both the donor and the recipient). Patients undergoing live-donor kidney transplants >19 years of age will be enrolled in this study. Perioperative immunosuppressive agents will be administered according to the institution protocol, and all patients will undergo general endotracheal anesthesia.

#### **4.1 Randomization and intervention**

Patients undergoing live-donor renal transplant will be randomized to the RIPC or the control group in a 1:1 ratio using manually shuffled blocks of ten generated by the study coordinator. The allocation sequence will be concealed until the study group is assigned. The study coordinator will open the opaque sealed envelope containing the patients' group before the patient arrives at the operating room. For patients randomized to RIPC, a tourniquet (Stryker, Kalamazoo MI) will be placed on the lower or upper extremity avoiding the intraoperative blood pressure cuff and any functioning dialysis-access fistula. The

tourniquet will be inflated 3 times to a pressure of 200mmHg for five minutes with five minutes of reperfusion between inflations. The RIPC regimen will be administered while patient monitors, intravascular catheters and indwelling bladder catheters are being placed in order not to affect the time from induction of anesthesia to initial skin incision compared with the control group. Tourniquet cuff pressures of 20 mmHg applied to control group patients will provide some level of compression without ischemia. All patients will receive standard perioperative and postoperative care as directed by the anesthesiology and surgical staff with all receiving isoflurane as part of the anesthetic technique.

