#### **4.4 Statistical Analysis**

The sample size calculation is based on a projected difference of NGAL levels between the two study arms. Hall et al reported a mean NGAL level of 49 mg/mL (SD = 37 mg/mL) for a group of patients that had immediate graft function and a mean NGAL level of 248 mg/mL in a group of patients with slow graft function. (which Hall reference is this) Based on these data we consider a conservative estimate of a mean difference between study groups to be 35 mg/mL NGAL. Using these assumptions, an alpha level of 0.05 and 80% power, we calculate a sample size of n= 19 per study group. Variables such as biomarkers, blood pressure, creatinine, and urine output that are expressed at multiple time points will be compared between the groups using repeated measures of ANOVA. Categorical variables will be expressed as percentages and will be compared using chi-squared analysis. A  $p$  value  $<0.05$  will be considered to be a statistically significant difference.

Ref#1 Perico(2004) delayed graft function in kidney transplantation Lancet 364(9447): 1814-1827 Perico, N., et al. (2004). "Delayed graft function in kidney transplantation." Lancet **364**(9447): 1814-1827

Ref #2 (old ref #11)

Ref#3 Rabb,H(2012) The promise of immune cell therapy for acute kidney injury.journal of clinical investigation122(11):3852-54(old ref #38)

Ref#4 Perico P (2004) Delayed graft function in kidney transplantation Lancet 364(9447):1814-1827

Ref#5 Siedlecki a etal(2011) Delayed graft function in kidney transplant Am j Transplant 11 (11) :2279-2296(old ref#42)

Ref#6 (OLD REF#6)

i Perico, N., et al. (2004). "Delayed graft function in kidney transplantation." *Lancet* **364**(9447): 1814-1827

ii Eltzschig ,H k and T.Eckle (2011). Ischemia and reperfusion –from mechanisms to translation *Nature Medicine* **17**(11) :1391-1401

iii Rabb,H(2012). The promise of immune cell therapy for acute kidney injury.*journal of clinical investigation***122**(11):3852-54

iv same as #1. Perico, N., et al. (2004). "Delayed graft function in kidney transplantation." *Lancet* **364**(9447): 1814-1827

v Siedlecki a etal. (2011). Delayed Graft Function in Kidney Transplant. *Am j Transplant* **11** (11) :2279-2296

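### The study coordinator both makes the hand-shuffled blocks of ten and opens the envelopes, so concealment is not assured for that role

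*Combined protocol and SAP*

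**What the plan says.** Section 4.1 (Randomization and intervention) has patients "randomized to the RIPC or the control group in a 1:1 ratio", "using manually shuffled blocks of ten generated by the study coordinator". It then states: "The allocation sequence will be concealed until the study group is assigned". The next sentence reads: "The study coordinator will open the opaque sealed envelope containing the patients' group before the patient arrives at the operating room".

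Ten is the only block size given. Section 4.1 names nobody other than the coordinator to produce the sequence, or to prepare, seal or hold the envelopes. It does not say that envelopes are numbered or that openings are recorded. Section 4 (Experimental Design) requires consent from donor and recipient, but the order of consent and envelope opening is not given. The documents do not say who screens, approaches or enrols patients.

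On size, section 4.4 (Statistical Analysis) states: "we calculate a sample size of n= 19 per study group". That is 38 in total.

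**The concern.** Opaque sealed envelopes hide the next assignment from people who did not prepare them. They give less protection against the person who prepared them, and section 4.1 gives preparing the sequence and opening the envelopes to one role. Whoever opens every envelope also knows the running count in each block, and with a single block size of ten the end of each block becomes predictable.

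Anyone who can foresee an assignment and can also affect who enters the trial, or in what order, can place better-prognosis patients in one arm, knowingly or not. The analysis would be poorly placed to correct this. Section 4.2 lists no urinary biomarker sample before the intervention, because time zero is the end of surgery. Section 4.4 names repeated-measures ANOVA and chi-squared tests and no covariate adjustment. With 19 per group, a few steered cases can move a mean.

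**Working it through.** **Inputs.** From section 4.1: 1:1 allocation, blocks of ten, one role generating the sequence and opening the envelopes. From section 4.4: 19 per group, "an alpha level of 0.05 and 80% power", a difference of 35 and an SD of 37 (units as printed). Sidedness is not stated, so I assume two-sided.

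**1. The plan's sample size.** The normal approximation gives n = 2 × (1.960 + 0.842)² × (37/35)² = 17.5, so 18 per group. The two-sample t-test gives 18.55, rounded up to 19, with power 0.81 at 19. The stated figure reproduces. It does not depend on the allocation method and is used here only to fix the total at 38, which is three full blocks plus 8 places of a fourth.

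**2. Reading A: the coordinator knows the order.** All 38 of 38 assignments are known in advance.

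**3. Reading B: envelopes are sealed and then shuffled, so the order is unknown.** The coordinator still knows the block size and every assignment already opened.

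*Certain assignments.* Place j is certain when one arm's five places have all gone in the first j − 1 draws. The probability is 2 × C(j − 1, 5) / C(10, 5), with C(10, 5) = 252.

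| Place in block | Probability that it is certain |
|---|---|
| 6 | 2/252 |
| 7 | 12/252 |
| 8 | 42/252 |
| 9 | 112/252 |
| 10 | 252/252 |

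- Full block: 420/252 = 10/6 = 1.67 of 10.
- First eight places only: (2 + 12 + 42)/252 = 0.22.
- 38 patients: 3 × 1.67 + 0.22 = 5.2 certain assignments.

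*Correct guesses.* The best strategy is to guess the arm with more places left.

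- Full block: 5 + (2¹⁰/C(10, 5) − 1)/2 = 5 + (1024/252 − 1)/2 = 6.53 of 10, or 65.3%, against 50% by chance.
- Place 9 is guessed correctly with probability 112/252 + ½ × 140/252 = 0.722, and place 10 always. The first eight places therefore give 6.532 − 0.722 − 1 = 4.81.
- 38 patients: 3 × 6.532 + 4.81 = 24.4, or 64.2%, against 19 by chance.

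**4. Largest bias on reading B.** Let p be the proportion guessed correctly and D the mean prognostic difference between the patients placed when one arm is expected and those placed when the other is. If every guess is acted on, the expected difference between arms is about pD − (1 − p)D = (2p − 1)D.

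- Full blocks: 2 × 0.653 − 1 = 0.31, so 0.31 D.
- 38 patients: 2 × 0.642 − 1 = 0.28, so 0.28 D.

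The documents give no value for D, so I put no figure on the bias in NGAL units. This ceiling belongs to reading B. On reading A, p = 1 and the formula gives D itself.

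**The case against.** The strongest reply is that shuffling by hand, taken together with opaque sealed envelopes, can fairly mean that envelopes were sealed first and then mixed, so that even their preparer does not know the order. The text allows this. A reader might infer from the shared role that concealment fails completely for the coordinator. The documents do not support that, because they never say the coordinator knows the order. The reply does not remove the point, however: reading B still leaves block ends predictable to the person opening the envelopes.

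The second reply is that foreknowledge does harm only if its holder can act on it. No section says that the coordinator screens, consents, enrols or schedules patients. A reader might also suppose that live-donor surgery, being booked ahead, leaves room to choose which pair goes next. The documents describe no scheduling, and advance booking could equally restrict reordering. This reply stands. The route to bias is possible but not shown, and the 0.28 to 0.31 factor is a ceiling that requires a suitable patient at every place.

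Third, silence about a log or retained envelopes does not mean that none will be kept. That also stands. What can be said is that a hand shuffle cannot be reproduced and that section 4.1 describes no record of it.

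**Conclusion.** Section 4.1 does not separate making the sequence from opening the envelopes, and its single block size leaves part of the sequence predictable on either reading. Concealment is therefore not assured for the coordinator: between about 5 of 38 assignments (reading B) and all 38 (reading A) can be known for certain in advance. On reading B, about 64% to 65% can be guessed correctly.

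This rests on two readings of the text: that the same singular role means one person in both sentences, and that ten is the only block size because no other is given. Selection bias needs the further assumption that the coordinator influences who is approached or in what order.

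It would go too far to conclude that allocation will be steered, or that concealment fails for surgeons, anesthesia staff or patients. Nothing in the documents shows either. The sample size, alpha and power are unaffected. This is a cheap improvement, to be made before the first allocation because the analysis cannot reliably repair steering afterwards.

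**What to change.** In section 4.1, replace the hand-shuffled blocks with a computer-generated 1:1 list that uses randomly mixed block sizes not disclosed to recruiting staff. Have an existing team member who neither recruits patients nor opens envelopes make the list and seal it in sequentially numbered opaque envelopes. The coordinator may still open them, but takes the next number only after the donor-recipient pair has consented and been logged. Keep the list for audit, and state who enrols.

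The cost is a small amount of existing staff time and an edit to section 4.1. Mixed blocks can leave the arms uneven by a few patients at the end. The current scheme does not guarantee 19 and 19 either: stopping eight places into the fourth block gives 20 and 18 with probability 112/252, or 44%.

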#### **4.3 Outcomes**

The degree of allograft injury will be assessed by the levels of urinary biomarkers NGAL, IL-18, and KIM-

1. The primary endpoints will be the level of graft function in the early post transplantation period categorized as follows: delayed graft function (DGF) (defined as the need for dialysis within the first week of transplantation), slow graft function (SGF) (defined as <40% decrease in serum creatinine by POD 3), and immediate graft function (IGF) (defined as >40% reduction in serum creatinine by POD3). Incidence of allograft primary malfunction will be based on urine output during the first three days after

transplantation, the one month serum creatinine concentration, one month estimated GFR calculated according to diet modification. Additional secondary endpoints include 90 day mortality, length of ICU stay, and length of hospital stay.

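### The plan has a sham cuff but does not hide the cuff or the arm from the staff who direct care, so the dialysis-defined DGF class of the primary endpoint is open to bias

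*Combined protocol and SAP*

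**What the plan says.** Section 4.1 describes the active procedure as follows: the "tourniquet will be inflated 3 times to a pressure of 200mmHg for five minutes with five minutes of reperfusion between inflations". For controls it says only: "Tourniquet cuff pressures of 20 mmHg applied to control group patients will provide some level of compression without ischemia". It does not give the number or duration of sham inflations.

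On timing, 4.1 says: "The RIPC regimen will be administered while patient monitors, intravascular catheters and indwelling bladder catheters are being placed", and gives the reason as "in order not to affect the time from induction of anesthesia to initial skin incision compared with the control group". Section 4 adds that "all patients will undergo general endotracheal anesthesia".

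On care, 4.1 says: "All patients will receive standard perioperative and postoperative care as directed by the anesthesiology and surgical staff". Section 4.3 makes the primary endpoint a three-way class of early graft function. DGF is "defined as the need for dialysis within the first week of transplantation". Slow and immediate graft function (SGF, IGF) are separated by whether serum creatinine has fallen by 40% by postoperative day 3.

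On knowledge of the arm, 4.1 says that the sequence stays concealed until assignment and that the study coordinator opens the sealed envelope before the patient reaches the operating room. No section names a blinded party. The only mention of double blinding, in 2.2.4, describes a cited contrast-nephropathy trial.

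**The concern.** Concealing the sequence until assignment protects the allocation. It gives no protection once the envelope is open. From then on the sham cuff is the plan's only measure of a blinding kind, and the text gives it none of the features that would make it work as one. Anyone at the cuff or its gauge can tell 20 mmHg from 200 mmHg. A cuff held at constant low pressure can also be told from one that inflates and deflates three times, even with the gauge covered.

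The plan assigns perioperative and postoperative care to the anesthesiology and surgical staff and does not keep the arm from them. It does not say who decides on dialysis, how need is judged, or whether those who decide know the group. If they know it, the decision that defines DGF can be influenced in either direction. Fluid and diuretic management can also shift urine output, and discharge decisions can shift length of ICU and hospital stay. A difference between arms in these outcomes could then not be attributed with confidence to RIPC.

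**Working it through.** **Inputs.** DGF in 4-10% of live-donor transplants (2.1 Background); 19 per group, alpha 0.05, 80% power, mean difference 35, SD 37, chi-squared test for categorical variables (4.4 Statistical Analysis); 1:1 allocation (4.1).

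**Step 1: the plan's own figure.** The sample size rests on NGAL, not on DGF. With a two-sided test (assumed, as 4.4 does not state sidedness), the normal approximation is n = 2 x (1.960 + 0.842)^2 x 37^2 / 35^2 = 17.5, so 18 per group. The two-sample t-test calculation gives 18.55, so 19, which matches 4.4. The trial therefore has 2 x 19 = 38 recipients.

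**Step 2: expected DGF cases.** 38 x 0.04 = 1.5 and 38 x 0.10 = 3.8 in total, or 0.76 to 1.9 per arm. The chance of no case at all is 0.96^38 = 21% at the low rate and 0.90^38 = 1.8% at the high rate.

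**Step 3: how sensitive a DGF yes/no comparison is.** Pearson chi-squared without continuity correction, 19 per arm:
- 0 v 3: expected 1.5 DGF and 17.5 non-DGF per arm; 2 x 1.5^2/1.5 + 2 x 1.5^2/17.5 = 3.26; p = 0.071.
- 0 v 4: expected 2 and 17; 2 x 2^2/2 + 2 x 2^2/17 = 4.47; p = 0.034.

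One further dialysis case crosses 0.05 here, but the table is an extreme one. Three limits apply:
- Every case must fall in one arm, and a total of 4 is just above the top of the expected range.
- The expected DGF count is 2 per arm, where the uncorrected test is unreliable. Fisher's exact test for 0 v 4 gives 2 x C(19,4)/C(38,4) = 2 x 3876/73815 = 0.105.
- The endpoint has three classes. With DGF 0 v 4, SGF 2 v 2 and IGF 17 v 13, the statistic is 4 + 0 + 2 x 2^2/15 = 4.53 on 2 degrees of freedom, p about 0.10. Other SGF splits give other values.

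**Step 4: illustration of bias.** The size of any bias is an assumption; the documents give none. Suppose RIPC has no effect and knowledge of the arm adds d to the probability of dialysis in controls. The rejection rate is the sum, over all pairs (i, j) with uncorrected p < 0.05, of Bin(i; 19, p + d) x Bin(j; 19, p).

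| Base rate p | d = 0 | d = 5 points | d = 10 points | d = 20 points |
|---|---|---|---|---|
| 4% | 0.6% | 4% | 14% | 44% |
| 10% | 3.6% | 7% | 13% | 34% |

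This treats DGF as yes/no. A small bias does little to the false-positive rate; a moderate or large one raises it well above 5%.

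**The case against.** The strongest reply is that the documents are silent, and silence does not show that people are unblinded. They do not say who is present when the cuff is used, who works it, or whether the gauge can be seen. They do not name who decides on dialysis, and that could be a team that never saw the cuff. This stands. A reader might infer that the sham protects nobody whose decisions affect the endpoint; the text does not support that.

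A reader might also infer that the patient is already anaesthetised, so that the sham has no use except to mask staff. The reference to induction-to-incision time makes anaesthesia likely, but 4.1 does not state it. The regimen takes about 25 minutes (3 x 5 of inflation plus 2 x 5 of reperfusion), and part could precede induction, in which case the sham would help to blind patients. The sham can also serve as a physical control for compression, which is how 4.1 describes it.

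Third, only DGF rests on a decision. At 4-10% DGF, most patients will be classed as SGF or IGF by a creatinine value. The biomarkers, on which the sample size rests, are laboratory measurements. This also stands, with two limits: open management of fluids can still affect creatinine and urine measures, and 4.2 says that assays are run in batches but not that the laboratory is unaware of the arm.

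None of this supplies the missing protection. Followed literally, the plan allows the arm to be seen and passed on.

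**Conclusion.** The concern holds in this form: the plan specifies a sham cuff but does not hide the pressure or cycle, does not keep the arm from the staff who direct care, and does not say who is blinded. The DGF class of the primary endpoint is therefore open to bias, as are, secondarily, urine output and length of stay. The SGF/IGF split and the biomarkers are less exposed.

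The size cannot be given as a bias, because the documents hold nothing to estimate one from. What can be said is that 1.5-3.8 DGF cases are expected, assuming the 4-10% rate in 2.1 applies to this population and all 38 are analysed, so a few influenced decisions could change how that class reads. It would be tempting to say that one dialysis decision decides the trial. That holds only for a chosen yes/no table under the uncorrected test, and it disappears with Fisher's test or with the three-class table shown above. The point is worth acting on because the remedy is cheap and masking cannot be added later for patients already treated.

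**What to change.** In 4.1, state who is blinded, and add that:
- the sham follows the same inflation and deflation timing as the active regimen, since a covered display alone does not hide a constant cuff from a cycled one;
- the study coordinator, who already knows the allocation, operates the tourniquet with the display covered and the limb draped in both arms;
- the group is not entered in the anaesthesia record or the chart.

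In 4.3, state that the staff who decide on dialysis and the assay laboratory are not told the group until the data are locked. If those deciding on dialysis are already a separate team, one sentence saying so, with the rule that they are not told the arm, settles that part.

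For the sham to match the active regimen, the regimen must be consistent. The Specific aim gives a cycle count in which four is followed directly by five, and applies the procedure to donor and recipient. Section 4.1 gives three inflations and does not say whether donors are included. These passages must be reconciled, and any donor sham described.

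The cost is wording, a cover and drape, and coordinator time in the operating room: about 25 minutes per application on the 4.1 regimen, and more if donors are included. Masking of the anaesthetist may remain incomplete, and the protocol should say so.
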